The study is a prospective, randomized, multi-center trial designed to demonstrate the safety and efficacy of the C-Pulse[®] System in relieving heart failure symptoms in patients with ACC/AHA Stage C, NYHA Class III to ambulatory Class IV heart failure. Reduction in heart failure symptoms will be demonstrated by increased freedom from heart failure related hospitalization or death in subjects implanted and treated with the C-Pulse System as compared to a concurrent, randomized control group receiving standard optimal medical therapy (OMT).

Patients will be enrolled into the trial upon providing informed consent. Procedures related directly to the study must not be performed prior to informed consent. Following confirmation of subject eligibility, subjects will be randomized to one of two treatment arms, Treatment or Control, in a 1:1 allocation utilizing a random permuted block design stratified by study center. The Treatment group subjects will receive the C-Pulse[®] System with immediate therapy following implant and OMT while the Control group will continue on OMT. The subjects will not be allowed to cross-over from the assigned group (i.e. a control will not be allowed to receive a C-Pulse). If a treatment subject is explanted, it will be reported in the study analysis per the statistical methods section.

This study will include up to 40 centers in the US and potentially some Canadian centers. The study population will include 388 patients. All subjects who meet eligibility requirements and sign study consent will then be randomized following the baseline testing completion. The follow-up period will be for a minimum of 12 months to assess the safety and efficacy. To facilitate the analysis of the therapeutic effect, it is desired that the system be used all the time. The subject must limit disconnection to a minimal amount of time allowed for personal convenience such as hygiene. The Driver logs subject usage automatically and stores this usage into the system files.

Subjects will be followed for up to five years.

If a subject undergoes anesthesia for the purpose of C-Pulse implantation but does not receive a C-Pulse System, the subject will be followed for 30 days for safety or until they are discharged, whichever occurs first.

[figure not shown]

Figure 1. Study Design Flowchart

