Prior to enrolling patients, each investigational center IRB will be required to approve the study Investigation Plan and the Patient Informed Consent. In addition, patients will be required to provide written informed consent for enrollment.

Patients will undergo a pre-implant baseline assessment to ensure they meet the inclusion and exclusion criteria prior to randomization. The baseline assessment must occur within 30 days prior to implant. Patient informed consent must be signed prior to conducting any screening or baseline testing procedure performed solely for study purposes. A screening number will be assigned upon consent. To minimize the burden to the patient, data collected as standard of care and not for the specific reason for assessing study eligibility may be used for baseline data points as outlined in the informed consent. These tests will suffice for the respective portion of the baseline dataset if collected within the pre-implant evaluation prior to randomization.

When a subject has met all Inclusion/Exclusion Criteria for the study, he/she will be randomized and assigned a randomization number by the center. The treatment subjects must proceed to implant within the window (≤ 30 days from consent to implant).

If the subject does not meet the inclusion/exclusion requirements, he/she will be study exited.

In accordance with the ethical principles that have their origin in the Declaration of Helsinki, each subject must be informed about the study and the patient or legal representative must sign and date an agreement acknowledging that participation in the study is voluntary. The Patient Informed Consent Form will be provided to the patient in the language he/she is able to read and understand. (Refer to Appendix E for the sample Consent Forms). The original signed Informed Consent will be retained in the individual Participant Study folders, and copies of the signed Informed Consent Form will be provided to the patient and to the hospital medical records of the patient.

Patients shall be consented for follow-up to five years.

Subject Withdrawal or Loss to Follow-Up

In the event a subject chooses to withdraw from the clinical study, the investigational site should attempt to ensure that any adverse events are resolved and documented as such. A Study Exit record must be completed and the subject will no longer be followed in the clinical study.

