In the event the subject becomes lost to follow-up, the investigational site should make two documented attempts to contact the subject. A Study Exit record must be completed and the subject will no longer be followed in the clinical study.

Data Collection Overview

A review of patient files is required to determine preliminary eligibility according to patient inclusion and exclusion criteria. Baseline data including functional tests must be collected no more than **30** days prior to randomization. Baseline imaging such as echo and CT scans must be collected no more than 90 days prior to randomization. See the data collection table for details.

Follow-up data will be collected at the time of implant, hospital discharge, at planned follow-ups (6 week, 3, 6, 12, 18-month and annually from the implant date thereafter up to 5 years). All serious adverse events will be collected throughout the study until closure.

All study subjects will follow the prescribed follow-up scheduled despite randomization. Day 0 for the treatment group will be the day of implant. Day 0 for the Control Group will be the day of randomization. Each group will continue with optimal medical therapy for the duration of the study, including all standard of care medications and treatments including transplant, VAD, etc. If the subjects are transplanted or placed on another device they will be censored from the primary endpoint analysis and study exited. Subjects implanted with the C-Pulse will be followed until device removal. If the PIL is explanted and not replaced, the subject will be followed for safety until removal of the entire system.

Data will be collected via electronic data capture (EDC) screens referred to as e-case report forms (eCRFs). Echocardiogram tapes and digital storage media must be documented in the patient medical record for source documentation.

Table 1, below outlines the data collection with the appropriate follow-up time windows.

Table 1. Follow-up Windows

Evaluation	Time Window
Pre-Implant Evaluation	No more than 30 days prior to implant
Randomization	Post Baseline Testing and Pre-Implant
Implant	Day 0 (Treatment Group) – Implant Day 0 (Control Group) – Randomization
Pre-Discharge	Within 36 hours prior to discharge
6 – week follow-up	Days 42 ± 7 Post-Implant
3 – month follow-up	Days 90 ± 14 Post-Implant
6 – month follow-up	Days 180 ± 30 Post-Implant
12 – month follow-up	Day 365 ± 30 Post-Implant
18 – month follow-up	Day 540 ± 30 Post-Implant

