Any serious adverse effect on health or safety or any life-threatening problem or death caused by, or associated with, the device, if that effect, problem or death was not previously identified in nature, severity, or degree of incidence in the protocol or application (including a supplementary plan or application), or any other unanticipated serious problem associated with a device that related to the rights, safety, or welfare of subjects. [21 CFR 812.3 (s)]

Device Deficiency

A device deficiency is defined as; inadequacy of a medical device with respect to its identity, quality, durability, reliability, safety and performance. Device deficiencies must be reported on a device deficiency eCRF.

(Note: Device deficiencies include malfunctions, use errors, and inadequate labelling).
[ISO 14155:2011]

Subject Deaths

All subject deaths must be documented in the database. If the subject dies during the study, notify the Sunshine Heart Inc. field support personnel as soon as possible upon first learning of the death. Follow any IRB requirements for reporting of deaths or adverse events.

In the event of a subject death, efforts should be made to retrieve the implanted device and to obtain an autopsy in order to assess the state of the heart and aorta. A sample of the aorta both beneath and adjacent the C-Pulse® Cuff should be collected for analysis. Please call Sunshine Heart Inc. Clinical Support for more instruction. For subjects who do not undergo autopsy, written documentation from the investigator will be required regarding circumstances as to why an autopsy was not performed. The device will be analyzed by local staff and Sunshine Heart Inc. Clinical Support personnel according to a standardized device retrieval protocol.

A death summary and an autopsy report are required. The report should be sent to Sunshine Heart Inc. upon completion and will be provided to the adjudication committee.

Explant Handling and Final Device Disposition

Promptly call Sunshine Heart Inc. Clinical Support for instruction regarding Explant Handling. Cultures should be taken from the device implantation site along with visual analysis and photographs when possible. If a piece of aortic tissue is available from underneath or adjacent to the C-Pulse Cuff, please send to pathology for histological studies. Explanted products should be returned to Sunshine Heart Inc. for analysis.

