Report all associated adverse events. Update the device tracking records with all products. If the device is not returned to Sunshine Heart Inc., justification must be provided in the log.

Subject Withdrawal and Study Exit

A Study Exit record shall be completed if subject is unable to or refuses to continue participation in the study. Notify the Sunshine Heart clinical support team as soon as possible upon learning of a subject withdrawal/study exit.

If the subject fails to comply with follow-up visits, the study center must make repeated attempts to contact the subject. Each attempt to contact the subject must be documented in the subject's records and in the database.

If the subject officially withdraws from the study, the investigator will document the reason for withdrawal and indicate any relationship of the withdrawal to the study or the device on the eCRF.

If a subject withdraws from the study at any time, there will be no penalty or loss of future medical care.

STATISTICAL METHODS AND DATA ANALYSIS

Analysis Population

All randomized subjects will be included in the evaluation of the primary efficacy objective. Subjects will not be allowed to cross-over. All subjects implanted with the C-Pulse System will be included in the evaluation of the primary safety objective. In the event a randomized subject does not receive the implant or does not receive the randomized therapy, the subject will be analyzed according to the randomized assignment for the primary analyses. Additional supporting analyses of the primary efficacy endpoint will be conducted (as treated and per-protocol) which exclude subjects who do not receive the randomized treatment or those with major protocol deviations. The defined analysis cohorts are:

- Intent to treat: All randomized subject irrespective of treatment actually received (primary efficacy analysis)
- As treated: All randomized subjects receiving treatment as randomized
- Per protocol: All randomized subjects without major protocol deviations

Primary Efficacy Endpoint

The primary efficacy endpoint is defined as freedom from worsening heart failure related hospitalization, LVAD implant, heart transplant, and death.

The primary efficacy endpoint includes all occurrences of worsening heart failure events and will be analyzed utilizing a multiple failure time analysis.

Hypotheses

H_0 : HR=1,

H_A : HR \neq 1,

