The total days alive and out of hospital following randomization through 12 months will be computed for each subject. Each subject will contribute a maximum of 365 days alive and outside of hospital following randomization. Days the subject is in hospital will be subtracted from the maximum. For subjects with a death or study exit prior to 12 months, the days from the date of death or study exit to the date at 365 days post randomization will be subtracted from the total. The treatment groups will be compared under the following hypotheses.

Hypotheses:

$$H_0: DT = D_c$$

$$H_A: DT \neq D_c,$$

where DT represents the distribution of days alive and out of hospital for Treatment and D_c the distribution of days alive and out of hospital for Control. Details of the analysis methods can be found in the Statistical Analysis Plan.

6. Improvement in KCCQ Score at 12 months

The improvement in overall KCCQ score will be computed as the difference between the baseline and follow-up scores at 12 months. Subjects not evaluated at 12 months due to prior VAD implant, heart transplant or death will have the worst possible outcome imputed for improvement. Improvement at 12 months will be compared between treatment groups under the following hypotheses.

Hypotheses

$$H_0: DT = Dc$$

$$H_A: DT \neq Dc,$$

where DT represents the distribution of improvement in Overall KCCQ Score for Treatment and Dc the distribution of improvement in Overall KCCQ for Control. Details of the analysis methods can be found in the Statistical Analysis Plan.

Additional Supportive Analyses

1. Components of primary efficacy endpoint

The components of the primary endpoint will be summarized individually by treatment group. The proportions of subjects with heart failure related hospitalization, LVAD implant, heart transplant, and death due to worsening heart failure will be reported and the time to each event will be described by Kaplan-Meier curves. The number and proportion of subjects with hospitalization due to worsening heart failure as well as the rate per patient year will be summarized.

2. All-cause mortality

All-cause mortality will be summarized by treatment group by number and percent of subjects as well as by Kaplan-Meier curves.

3. Major cardiac events

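### Follow-up for death stops at study exit, at two points in the treatment arm only, so the all-cause mortality summary by arm can miss deaths unequally

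*Combined protocol and SAP*

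**What the plan says.** **Exits that apply to both arms.** Under *Subject Withdrawal or Loss to Follow-Up*, withdrawal and loss end with the same instruction: "A Study Exit record must be completed and the subject will no longer be followed in the clinical study". For loss, the step before it is that "the investigational site should make two documented attempts to contact the subject". *Subject Withdrawal and Study Exit* says instead, for missed visits, that "the study center must make repeated attempts to contact the subject". *Data Collection Overview* adds: "If the subjects are transplanted or placed on another device they will be censored from the primary endpoint analysis and study exited".

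**Stops that apply to the treatment arm only.** *Data Collection Overview* states: "Subjects implanted with the C-Pulse will be followed until device removal". Under *Design*, if a subject is anesthetized for implantation but receives no device, "the subject will be followed for 30 days for safety or until they are discharged, whichever occurs first".

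**What is done with deaths.** *Subject Deaths* opens with "All subject deaths must be documented in the database", but the sentence after it concerns a subject who dies during the study. Serious adverse events are collected until closure, with no statement that this reaches subjects who have exited. Item 2 of *Additional Supportive Analyses* reads: "All-cause mortality will be summarized by treatment group by number and percent of subjects as well as by Kaplan-Meier curves". *Analysis Population* defines intent to treat as all randomized subjects, whatever treatment they received.

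**The concern.** The primary safety endpoint is measured in implanted subjects only, against a fixed goal of 0.60. It counts only events adjudicated as definitely related that lead to surgical intervention or death. The all-cause mortality summary is therefore where a reader would compare deaths between the randomized arms without relying on attribution.

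That comparison needs deaths to be found equally well in both arms, and the exit rules work against this in two ways. First, withdrawal, loss, VAD and transplant are unlikely to be independent of prognosis, and the trial is open-label, so their frequency may differ by arm. Second, device removal and anesthesia without implant can occur only in the treatment arm, so deaths missed through those two stops come only from that arm. A control subject has no matching stop.

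The LVAD study that the protocol calls an appropriate safety comparison followed patients whether or not they were transplanted or explanted (*Justification for Primary Safety Endpoint Sample Size*).

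**Working it through.** **Inputs from the documents**
- N = 388; attrition 10% per year; control event-free proportion 0.72 at six months; hazard ratio 0.70; accrual 2.5 years; minimum follow-up 12 months (*Primary Efficacy Endpoint Sample Size*).
- Reference cohort at six months: 84% alive; 64% alive and free of LVAD, transplant or inotropes (*Justification for Primary Efficacy Endpoint Sample Size Assumptions*).

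**Check of the plan's figure that uses attrition.** The control hazard is −ln(0.72)/0.5 = 0.657 per year. Schoenfeld's formula at HR 0.70, two-sided 0.05 and 80% power needs 247 events. With exponential hazards, uniform accrual and 10% attrition, the mean event probability is 0.624 to 0.627, so N is 394 to 396, within 3% of 388. The stated 265 events match 388 × 0.685 = 265.8, the case without attrition. That is a separate matter and does not bear on this point.

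**Model for missed deaths.** Constant competing hazards, the same in both arms:
- death: μ = −ln(0.84)/0.5 = 0.349 per year
- withdrawal or loss: a = −ln(0.90) = 0.105 per year
- VAD or transplant: g = −ln(1 − r)/0.5, with r = 0, 5%, 10% or 20% per six months (assumed)
- mortality after exit: kμ, with k = 0.5, 1 or 2 (assumed)

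With h = μ + a + g and horizon T:
- deaths seen = N(μ/h)(1 − e^(−hT))
- exits = N((a + g)/h)(1 − e^(−hT))
- missed deaths = N∫₀ᵀ (a + g)e^(−ht)(1 − e^(−kμ(T−t))) dt

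**One line by hand** (T = 1, r = 0, k = 1). h = 0.454 and 1 − e^(−0.454) = 0.365.
- Exits = 388 × (0.105/0.454) × 0.365 ≈ 33.
- Deaths seen = 388 × (0.349/0.454) × 0.365 ≈ 109.
- All deaths = 388 × (1 − 0.84²) = 388 × 0.294 ≈ 114, so about 5 are missed.

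**Results at 12 months, 388 subjects**

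| VAD/transplant per 6 months | Exits | Deaths seen | Missed, k = 0.5 / 1 / 2 | Share of all deaths |
|---|---|---|---|---|
| none | 33 | 109 | 3 / 5 / 10 | 2.6% / 4.8% / 8.3% |
| 5% | 62 | 104 | 6 / 10 / 19 | 5.1% / 9.2% / 15.3% |
| 10% | 90 | 99 | 8 / 15 / 28 | 7.6% / 13.5% / 21.8% |
| 20% | 141 | 89 | 13 / 25 / 45 | 13.0% / 21.9% / 33.4% |

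The losses grow with time. At 2.25 years (1 + 2.5/2, the mean planned follow-up at the end of the 12-month phase) and k = 1, the missed share is about 10% with attrition alone and 18%, 25% or 38% with VAD or transplant added.

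**Limits of the model.** The 20% row equals the gap 84 − 64 in the reference cohort. That gap includes inotrope use, which is not an exit here. It may also leave out patients who had an LVAD or transplant and then died. It marks the top of an illustrative range and is not a forecast. Exits through device removal or failed implant are left out because the documents give no rate for them. The table gives totals over both arms and does not estimate a difference between arms.

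**The case against.** The strongest reply is that this analysis is supportive and descriptive, with no test, success criterion or decision attached, and that other parts of the plan already show these exits. LVAD and transplant are reported individually by arm. Supportive item 9 is a competing-outcomes summary of transplant, VAD, recovery and death. Days alive and out of hospital subtracts all days after death or study exit. The walk, LVEF and KCCQ analyses impute the worst outcome after VAD, transplant or death. All of this is true, and it limits the weight of the point. None of it recovers a death that occurs after exit.

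Some stronger readings are tempting but not supported.
- *The subjects who exit are those most likely to die.* The documents give no mortality after withdrawal or loss. For LVAD, Table 4 shows 43 deaths in 133 (32%, horizon not stated), against about 29% at 12 months implied by the reference cohort. The background section calls transplant effective and says LVADs improve survival.
- *Everyone who leaves is counted as alive.* The text of item 2 gives neither the denominator of the percentage nor a censoring rule. The rule under *Handling of Missing Data* is written for the primary efficacy analysis.
- *The bias favors the device.* The two one-arm stops can hide only treatment-arm deaths, but withdrawal, VAD and transplant could run more heavily in either arm.

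The gap between two and repeated contact attempts is small, since two attempts are already repeated ones. It still leaves sites unsure when a subject may be declared lost.

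Finally, the consent pages and the separate SAP cited by the protocol were not available. A vital-status clause may exist there. If so, it would still have to be reconciled with the instruction to stop following exited subjects.

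**Conclusion.** The point holds as a cheap improvement. Read as written, the plan stops looking for deaths at exit, does so at two further points in the treatment arm only, and has no visible provision to restore vital status. The by-arm mortality summary can therefore be incomplete and unequal, in an unknown direction, which sits badly with an all-randomized population.

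At 12 months the plan's own attrition alone implies about 3 to 10 missed deaths (about 3% to 8%). With VAD and transplant added, the range is about 6 to 45 (5% to 33%). These figures rest on constant hazards, the reference cohort's 84% six-month survival in both arms, an assumed VAD or transplant rate of 5% to 20% per six months, and assumed mortality after exit of 0.5 to 2 times the reference rate. They show possible scale only. The documents do not allow an estimate of the bias between arms.

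**What to change.** 1. In *Design*, *Subject Withdrawal or Loss to Follow-Up* and *Data Collection Overview*, add: *Vital status and date of death will be collected for every randomized subject through the end of the trial, including after withdrawal from visits, loss to follow-up, VAD, transplant, explant or a failed implant, by telephone, medical records or public sources, unless the subject specifically refuses this.*
2. Require this check before a subject is declared lost, and reconcile the two contact attempts in one section with the repeated attempts in the other.
3. Base supportive analysis 2 on all randomized subjects with this follow-up, and state its denominator and censoring rule.
4. Check the consent form and the separate SAP for any existing vital-status clause, and align the texts.

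The cost is a consent sentence with IRB review at up to 40 US centers and any Canadian ones, one short form, and a call or records check for exited subjects. No treatment or visit changes. It should be done early, because permission and contact details are hard to recover after exit. Deaths will still be missed where status cannot be traced or the subject refuses.
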